1.1 Trial objective

Investigating the effect of riociguat (MK-4836) in patients with early pulmonary vascular disease, defined as either a) mean pulmonary arterial pressure (mPAP) ≥ 25 mmHg with pulmonary vascular resistance (PVR) ≥ 2 to <3 WU and pulmonary arterial wedge pressure (PAWP) ≤ 15 mmHg or b) mPAP 21 - <25 mmHg with PVR ≥ 2 WU, and PAWP ≤ 15 mmHg associated with connective tissue disease (CTD) or as idiopathic/heritable form.

Primary objective

- 1) To investigate the effect of riociguat (MK-4836) treatment on pulmonary vascular resistance in patients with early pulmonary vascular disease, defined as stated above as change from baseline to 24 weeks of treatment.

Secondary objectives

- 2) To investigate, whether treatment with riociguat (MK-4836) may improve further hemodynamic and clinical parameters in patients with early pulmonary vascular disease, defined as stated above as change from baseline to 24 weeks of treatment.
- 3) To assess safety and tolerability of riociguat (MK-4836) treatment in patients with early pulmonary vascular disease, defined as stated above as change from baseline to 24 weeks of treatment.

1.2 Trial design

Randomized (1:1), double-blind, placebo-controlled, multicenter, multinational study.

Investigator-Initiated-Trial (IIT)

After the pre-treatment phase, eligible subjects were randomized at Visit 1 in a 1:1 ratio to the following 2 treatment groups:

- riociguat (MK-4836) 1.0-2.5 mg group (titration between 1.0 mg and 2.5 mg tid according to individual tolerability)
- placebo group (placebo tid, sham-titration according to individual tolerability).

1.3 Randomisation, stratification, blinding and replacement of patients

Randomisation was performed by permuted block randomization, stratified by centre. Treatment was allocated by consecutive patient numbers for each centre with respective blinded medication included in the investigational medicinal product packages for each visit.

Patients and investigators were blinded to treatment assignment. The statistician will be blinded to treatment assignment during the statistical analysis. In case of dropout, loss to

follow-up, early withdrawal or other cases of incomplete data, patients were not replaced. However, patients were encouraged to perform their final assessment in case of early termination or withdrawal. The results will be included in the analysis.

1.4 Data collection and monitoring

Data was entered into a paper-based CRF which was monitored for data quality, consistency and completeness. The monitored data was forwarded to data management for database entry, data checks and queries to the study site. For database closure, all queries have to be addressed and closed.

2 Definitions of patient populations to be analyzed - Analysis sets

2.1 Definitions

Male and female patients with CTD or idiopathic/heritable early pulmonary vascular disease. Both an elevated mean pulmonary arterial pressure >20 mmHg and an increase of PVR >2 WU have been shown to be above the upper limit of normal and are associated with development of manifest PAH and impaired survival in CTD. As a placebo-controlled study would have seemed unethical in patients, who are in clear indication of targeted treatment, patients with manifest PAH according to the current definition could not be included in this study (combination of both mPAP ≥ 25 mmHg and PVR ≥ 3 WU and PAWP ≤ 15 mmHg).

Patients with early pulmonary vascular disease, indicated by either a) mPAP ≥ 25 mmHg with PVR ≥ 2 to <3 WU and PAWP ≤ 15 mmHg or b) mPAP $21-25$ mmHg with PVR ≥ 2 WU and PAWP ≤ 15 mmHg (see Group I / Nice Clinical Classification of Pulmonary Hypertension) (acc. to Simonneau et al. 2019) were eligible to be enrolled into this study. Both a) and b) represent one phenotype with early pulmonary vascular disease/pathology.

All patients randomized and treated will be valid for the intention-to-treat population, hence the numbers of patients in the safety and intention-to-treat populations will be identical. In the intention-to-treat analysis set, patients will be analysed according to the group allocation they were randomized into. The primary endpoint will be analysed in a complete case analysis.

As sensitivity analysis, multiple imputation for the primary endpoint will be performed and analyzed.

A randomized patient is valid for safety / intention-to-treat analysis, if at least one dose of study medication was administered.

A patient is valid for the per protocol analysis, if the patient is valid for the safety / intention-to-treat analysis and shows no major protocol deviations.

Major protocol deviations are:

1. Patients who do not meet the inclusion criteria
2. Administration of IMP not according to protocol (e.g. compliance less than 80% or greater than 120% (corresponding to an overdose))

The above specifications of the analysis populations are in accordance with the recommendations given in the ICH-E9 Guideline “Note for guidance on statistical principles for clinical trials”.

2.2 Application

The primary efficacy analysis will be performed in patients valid for intention-to-treat analysis. The per-protocol analysis will be supportive. The safety analysis set will be equal to the intention-to-treat analysis set.

3 Trial centres

[figure not shown]
Patient numbers included per centre.

Centre	Planned number of patients	Actual number of patients
Heidelberg, Germany	25	23
Dresden, Germany	5	0
London, England	20	3
Lille, France	4	3
Zurich, Switzerland	4	3
Graz, Austria	4	2
Linz, Austria	4	1
Naples, Italy	4	0
Oslo, Norway	Site considered but eventually not selected	
Total	70	35*

*Reduced sample size due to early termination of the study for strategic reasons.

4 Visit schedule

ESRA Phase IIa Study (n=70)

Screening	Randomization/Baseline	Phone visits	Maintenance Period	iPhone visits (WOCBP only)	End of DB Study (OL1)	Safety follow-up
Visit 0 (V0)	Visit 1 (V1)	Visit 1.1 - 1.4	Visit 2 (V2)	Visit 3 (V3)	Visit 3 (V3)	+30 days
[Day -28 till Day 0]	[Day 1]	[every 2 weeks] till week 8	[Week 12]	[Week 24]	[Week 28]	
- Informed consent	- In-/exclusion criteria	- Drug/sham titration***	- Clinical Evaluation	- Clinical Evaluation	- patient's well-being	
- In-/exclusion criteria	- Clinical Evaluation	- Concomitant medication	- Concomitant medication	- Concomitant medication	- Pregnancy test	
- Demographics	- Vital Signs incl. ECG	- Blood pressure	- Physical Examination	- Physical Examination	- Adverse Events	
- Medical history	- WHO FC	- Pregnancy testin	- Vital Signs incl. ECG	- Vital Signs incl. ECG	- Adverse Events	
- Concomitant medication	- 6MWD, Borg Scale	week 4 and week 8	- WHO FC	- WHO FC	- Adverse Events	
- Clinical Evaluation	- SF-36	- Adverse Events	- 6MWD, Borg Scale	- 6MWD, Borg Scale	- Adverse Events	
- Physical Examination	- Echocardiogram		- Hematology, Chemistry	- Hematology, Chemistry	- Adverse Events	
- Weight	- Patient diary		- NT-proBNP	- NT-proBNP	- Adverse Events	
- Vital Signs incl. ECG	- Physical Examination**		- Pregnancy test	- Pregnancy test	- Adverse Events	
- Lung function, DLCO	- Weight**		- Patient diary	- Patient diary	- Adverse Events	
- Blood Gas Analysis(BGA)	- Concomitant medication**		- Drug collected and dispensed	- Drug collected and dispensed	- Adverse Events	
- Hematology; Chemistry	- Blood Gas Analysis(BGA) **		- Adverse Events	- Adverse Events	- Adverse Events	
- NT-proBNP	- Hematology; Chemistry**					
- Pregnancy test (WOCBP only)	- NT-proBNP**					
- RHC*	- Initiation of study drug***					
- Adverse Events	- Adverse Events					

* RHC at screening only in patients who have not had a RHC within a month before OR within the preceding 6 months if clinically stable as stated
** not if already performed at Screening AND if Screening and Baseline are conducted during same hospital stay

***Titration Plan:
individual dosing titration

Overview of visit assessments

Assessments	Double-blind						
	Screening	Visit 1 Baseline	V 1.1-1.4 Phone Visits Titration	Visit 2 Interim visit	V 2.1-2.2 Phone Visits Only WOCBP	Visit 3 Termination visit	Visit 4 Safety FU
	-28 days	Day 1	Week 2, 4, 6 and 8 ±2 days	Week 12 ±7 days	Week 16 and 20 ±2 days	Week 24 ±14 days	30 days after last IMP intake ±14 days
Informed Consent	1	-	-	-	-	-	-
Inclusion / exclusion criteria	1	1	-	-	-	-	-
Patient diary(handing out / compliance check)	-	1	-	1	-	1	-
Prior and concomitant medication	1	1°	4	1	2	1	1
Demography, height and medical history	1	-	-	-	-	-	-
PAH classification, etiology, diagnosis date	1	-	-	-	-	-	-
WHO-FC	-	1	-	1	-	1	-
Vital signs, incl. heart rate, SpO ₂ (%)	1	1	-	1	-	1	-
6MWD, Borg Dyspnea Score	-	1	-	1	-	1	-
Weight	1	1°	-	1	-	1	-
ECG	1	1°	-	1	-	1	-
Blood gas analysis	1	1°	-	-	-	1	-
Lung function testing (Plethysmography)	1	1°	-	-	-	1	-
Diffusing capacity of the lung	1	1°	-	-	-	1	-
Right heart catheter	1*	-	-	-	-	1	-
Physical examination	1	1°	-	1	-	1	-
Laboratory Hematology, Chemistry, Hemostaseology, NT-proBNP	1	1°	-	1	-	1	-
Pregnancy test (only WOCBP)	1	1°¶	2+ (week 4 and 8)	1	2+ (week 16 and 20)	1	1+
Echocardiography	-#	1#	-	-	-	1	-
Quality of life (SF-36)	-	1	-	-	-	1	-
Adverse Events	1	1	4	1	2	1	1
Systolic blood pressure and dose adjustment	-	-	4	-	-	-	-
Drug dispensed	-	1	-	1	-	-	-
Drug collected	-	-	-	1	-	1	-
Drug compliance	-	-	-	1	-	1	-
Phone visits	-	-	4	-	2	-	1

* RHC at screening will only be performed in patients who have not had a RHC within the preceding 1 month at screening. A preceding RHC from the last 6 months can be used if the patient had no signs of clinical changes defined as change of 6MWD >10%, WHO-FC change or >30% change in NT-proBNP. RHC must have been measured in the participating center under standardized conditions.

+ Pregnancy test at home.

¶ Handing out pregnancy tests for home use

° Will not be performed if already performed at Screening AND if Screening and Baseline are conducted during same hospital stay.

† Optional during the SARS-CoV2-pandemic.

If, due to organisational reasons, echocardiography cannot be performed at Baseline, it can be performed during Screening period and it can be used as baseline value. Echocardiography cannot be performed after baseline.

5 Analysis variables

5.1 Efficacy Variables

The primary efficacy variable is the change of PVR from baseline to 24 weeks.

5.1.1 Sample size considerations

In this randomized study patients with early pulmonary vascular disease, indicated by either a) mPAP ≥ 25 mmHg with PVR ≥ 2 to < 3 WU and PAWP ≤ 15 mmHg or b) mPAP $21-25$ mmHg with PVR ≥ 2 WU and PAWP ≤ 15 mmHg were randomized into two groups: one group receiving riociguat (MK-4836) and one placebo group.

In the EDITA study (Pan et al. 2019) SSc patients with mildly elevated mPAP 21-24 mmHg showed a significant reduction of PVR after 6 months of treatment (control-group 0.02 ± 0.76 vs. intervention group -0.59 ± 0.79 WU; effect size 0.77). The changes in PVR were equal to a $23.87 \pm 35.68\%$ reduction in the intervention group and increase by $5.44 \pm 36.61\%$ in the control group (effect size 0.81).

A meta-analysis showed an effect size of 0.88 in both PAH and CTEPH (Zhao et al. 2019).

In the retrospective analysis of patients with CTD-APAH receiving riociguat in PATENT-1 and PATENT-2, mean improvement of PVR after 12 weeks was 132 ± 140 dynes*sec*cm $^{-5}$ in patients with SSc (equals 1.65 ± 1.75 WU; effect size 0.94; Humbert et al. 2017). Patients with SSc-PAH had an effect size of 0.97 (Humbert et al. 2017).

In this study, patients with PVR ≥ 2 WU were to be included. The use of the effect size of the EDITA study for sample size calculation leads most likely to an underestimation of the effect, as in this study with ambrisentan most patients showed a PVR < 2 WU at baseline. Furthermore, all studies reported in the table below had a study duration of 12 weeks. A study duration of 24 weeks will lead to a higher effect and reduction of PVR. Therefore, we assume an effect size of 0.87 of riociguat treatment in this study. A comparable effect size for both included subgroups is anticipated for this study.

Reference	Change / difference in PVR	Effect size	Power	Sample size without dropout
Pan 2019; EDITA	SSc: 0.61 ± 0.79 WU (Ambrisentan)	0.77	80%	56
Pan 2019; EDITA	SSc: $-23.87 \pm 35.68\%$ (n=17) in the intervention group and increase by $5.44 \pm 36.61\%$ (n=15) in the control (Ambrisentan)	0.81	90%	66
Zhao 2019 Meta-analysis Riociguat	PH (PAH and CTEPH): n=695 (Riociguat)	0.88	85%	50
Humbert 2017 CTD-APAH from PATENT-1 and 2	SSc: 1.65 ± 1.75 WU Other CTD: 3.45 ± 3.54 WU (Riociguat)	0.94 0.97	90% 90%	50 48
A sample size of 58 will lead to n=70 with dropout of 15%.				

With the sample size of 70 patients and a dropout of 15% (valid sample size n = 58), a 90.2% power will be achieved to reject the null hypothesis, if the true treatment effect is at least a 30% reduction of PVR and both groups have an equal standard deviation of 34.5%, according to the two-sample student's t-test, with a type I error of 0.05 (two-sided). A sample of 70 patients (35 patients in each group), allocated in a 1:1 ratio, was therefore aimed to be included.

The primary endpoint will be analyzed by an analysis of covariance (ANCOVA) with baseline values as covariates, which has a power advantage over the student's t-test, achieving a statistical power of 90.2% or more. If the preconditions for ANCOVA are not met, a student's t-test assuming unequal variances (Welch-test) will be performed.

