If the true treatment effect is at least a 30% reduction of PVR (effect size is 0.87), a sample size of 29 patients/group (total 58 patients) achieves a statistical power of 90.2% to reject the null hypothesis, according to the two-sample student's t-test, with a type I error of 0.05 (two-sided). With the sample size of 70 patients and a dropout of 15% (valid sample size n=58), we achieve a 90.2% power, if the means of PVR differ by at least 30% and both groups have an equal standard deviation of 34.5%. A sample of 70 patients (35 patients in each group), allocated in a 1:1 ratio, will therefore be included.

The primary endpoint will be analyzed by an analysis of covariance (ANCOVA) with baseline values as covariates, which has a power advantage over the student's t-test, achieving a statistical power of 90.2% or more. If the preconditions for ANCOVA are not met, a student's t-test assuming unequal variances (Welch-test) will be performed.

EudraCT: 2021-001633-40	Version 1.7 15.01.2025	ESRA
-------------------------	---------------------------	------

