7.8 Interim analyses

Not available

8 Deviations from the original protocol

The study was ended prematurely, leading to a sample size reduction to 35 patients (planned 70 patients).

The study was terminated early due to a strategic decision of MSD/Merck:

“After reviewing the timelines, remaining payments, and considering the changing landscape and altered feasibility of this study, a strategic prioritization was made to select this study for early termination.”

As a result of this decision, the final sample size reached 50% of the originally planned enrolment (n= 35). All statistical analyses will be conducted based on the available data at the time of study cessation. The reduction in sample size may limit the statistical power, particularly given the double blinded two-armed design of the study. According to the study protocol, patients were encouraged to perform their final assessment visit in case of any premature termination of study treatment or study participation. This data will be included into the final analysis according to the intention-to-treat principle.

Subgroup analyses may not be performed due to insufficient sample size.

9 Interpretation of results

Interpretation of data is limited by the early termination of the whole trial. This led to a reduction of sample size to 35 patients in total instead of per group, and to a premature study termination in a subset of patients. As the treatment effect is anticipated to be less distinct in a shorter period of time in the verum group and worsening of clinical parameters is expected to be less pronounced in the control group, early study termination will reduce the effect size and does therefore not bear the risk of overestimation of the clinical effects of the study treatment. A shorter study duration is expected to reduce the statistical power (reduction of sample size and effect size).

Safety data will comprise of less investigational medicinal production exposition than planned. As the study medication is already an approved treatment and extensive data on safety and tolerability is already available, a substantial impact on safety and tolerability results of the study is not anticipated.

Due to the reduced sample size, subgroup analyses such as centre effects may not be further analysed as sample sizes for each center and for hemodynamics subgroups are not high enough.

10 Data problems

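### SAP 5.1.1 still gives 90.2% power for the primary comparison, a planning value for 58 valid patients that was not restated after enrolment stopped at 35

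*SAP*

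**What the plan says.** SAP 5.1.1 (Sample size considerations) makes two power statements.

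- The first is conditional. With 70 patients, 15% dropout and 58 valid, "a 90.2% power will be achieved to reject the null hypothesis" for a 30% reduction of PVR and an SD of 34.5%, by two-sample t-test at two-sided 0.05. The paragraph closes by saying that a sample of 70, 35 per group, "was therefore aimed to be included".
- The second opens the next paragraph and describes the analysis still to be run: ANCOVA with baseline as covariate, more powerful than the t-test, "achieving a statistical power of 90.2% or more". This sentence names no sample size.

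The text comes from protocol 10.1, where the corresponding clause is "we achieve a 90.2% power, if the means of PVR differ by at least 30" percent. Protocol 10.1 puts the enrolment of 70 in the future tense and SAP 5.1.1 puts it in the past. The power clauses still look forward.

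Elsewhere the SAP reports the early stop:

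- The centre table in Section 3 totals 35, with the footnote "Reduced sample size due to early termination of the study for strategic reasons".
- Section 8 says "the final sample size reached 50% of the originally planned enrolment" and adds "The reduction in sample size may limit the statistical power".
- Section 9 says "This led to a reduction of sample size to 35 patients in total instead of per group". It expects less power, from both the smaller sample and a smaller effect in patients whose treatment was cut short.

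**The concern.** The only power figure in the SAP for the primary analysis belongs to a sample that was not reached. The SAP was written after the stop and partly edited for it, yet the ANCOVA sentence still attaches at least 90.2% to an analysis that will be run on 35 patients or fewer. Sections 8 and 9 give the direction of the loss and not its size.

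The size matters for reading the result. At 90.2% power, the chance of missing the planned effect is about 10%. On the same t-test inputs with the achieved sample, it is about 30% to 37%. A reader who takes the 5.1.1 figure at face value would give a non-significant result more weight against the planned effect than the sample supports.

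**Working it through.** **Inputs from the documents.** Two-sided alpha 0.05; difference 30%; SD 34.5%; planned 29 per arm (protocol 10.1), 58 in total (SAP 5.1.1); achieved total 35 (SAP Sections 3 and 8). The centre counts agree: 23 + 0 + 3 + 3 + 3 + 2 + 1 + 0 = 35. The primary analysis uses complete cases (SAP 7.5).

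**Inputs not in the documents, so assumed.** The split by arm: 18/17 if nobody is missing. The number of complete cases: 35 × 0.85 = 29.75, taken as 15/15, which carries over the planned 15% loss. The correlation r between baseline PVR and change in PVR.

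**Formula (t-test).** d = 30/34.5 = 0.87. Power is the probability that a noncentral t variable with n1 + n2 − 2 degrees of freedom and noncentrality d × √(n1·n2/(n1 + n2)) exceeds the two-sided 5% critical value in absolute size.

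| Sample | Noncentrality | df | Critical t | Power |
|---|---|---|---|---|
| 29/29 (plan) | 0.87 × √14.5 = 3.31 | 56 | 2.003 | 90.2% |
| 18/17 (35, none missing) | 0.87 × √8.743 = 2.57 | 33 | 2.035 | 70.4% |
| 15/15 (about 15% missing) | 0.87 × √7.5 = 2.38 | 28 | 2.048 | 63.3% |

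The first row reproduces the plan's figure exactly. The split has little influence: 20/15 gives 69.6%.

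**Effect needed for 90.2% by t-test.** d is about 1.13 at 18/17 and about 1.23 at 15/15, against 0.87 planned. At SD 34.5% these are differences of about 39% (1.13 × 34.5) and 42% (1.23 × 34.5).

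**Could ANCOVA make up the loss?** Adjusting for baseline shrinks the residual SD by √(1 − r²), so the effective d is 0.87/√(1 − r²), with n1 + n2 − 3 degrees of freedom. Solving for 90.2% gives:

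- r of about 0.64 at 18/17: 0.87/√(1 − 0.64²) = 0.87/0.768 = 1.13
- r of about 0.71 at 15/15: 0.87/√(1 − 0.71²) = 0.87/0.704 = 1.24

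This formula ignores chance imbalance in baseline PVR between arms. Simulations that include it put ANCOVA power up to 2 points lower, so the true thresholds are slightly higher. Neither document gives a value for r. At r = 0, ANCOVA power by the formula is 70.4% and 63.2%, in effect the t-test figures.

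**The case against.** The strongest reply is that 5.1.1 is planning text and reads as such. It stands under a sample-size heading, the first power sentence names 70 enrolled and 58 valid, and the past tense for the target of 70 marks it as the original aim. The ANCOVA sentence follows directly and repeats the same 90.2%, so in context it refers to the same 58 patients. The early stop is disclosed in Sections 3, 8 and 9, and centre and subgroup analyses are restricted because of it. A reader of the whole SAP would not believe that 35 patients give 90% power. Enrolment is over, and the confidence interval specified in 7.5 will show the precision achieved.

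Most of this stands. It limits the point to a missing label and a missing number. It does not remove the point: the ANCOVA sentence has no sample-size condition of its own and describes the analysis about to be run, and no section withdraws or replaces the figure.

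A reader might infer three stronger things that the documents do not support:

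- **That 90.2% was miscalculated.** It reproduces exactly at 29/29.
- **That the SAP conceals the loss of power.** Sections 8 and 9 state it.
- **That the ANCOVA cannot reach 90.2% with 35 patients.** This is not shown. A high enough correlation would allow it; the documents simply give no basis for assuming one.

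**Conclusion.** The point holds as a stale planning figure. For the sample that the SAP itself reports, t-test power at the planned effect size is about 63% to 70%, some 20 to 27 percentage points below the stated value (90.2 − 70.4 = 19.8; 90.2 − 63.3 = 26.9). The range rests on assumed counts of 18/17 and 15/15. ANCOVA power may be higher by an amount that cannot be derived from the documents. All these figures take the full planned effect; Section 9 expects a smaller one in patients stopped early, which would lower power further. The consequence is limited to how the result is read, because the primary analysis itself is unaffected. Correcting 5.1.1 is worthwhile but modest.

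**What to change.** In SAP 5.1.1:

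1. Label 90.2% as the original planning value for 58 valid patients, state that it does not apply to the achieved sample, and cross-refer to Sections 8 and 9.
2. Delete the ANCOVA power clause, or make it conditional on the planned 58 valid patients.
3. Add the t-test power at an effect size of 0.87 and two-sided alpha 0.05 for the actual complete-case counts per arm. On the counts assumed here it is about 70% (18/17) or 63% (15/15); the true counts should replace these.
4. Note beside that figure that ANCOVA power may be higher by an unknown amount, and that Section 9 expects a smaller effect in patients stopped early.

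A table of ANCOVA power by assumed correlation is not needed, since nothing in the documents supports one value over another.

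The cost is a few sentences in the SAP and a less favourable stated power. No patients are added, and the test, the estimate and the confidence interval stay as they are.
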